COVER PAGE

Title: Feasibility Study for Treating Trichotillomania With Wearable Device and

App System

NCT04241120

Document Date: 7/18/2019

STUDY PROTOCOL AND STATISTICAL ANALYSIS PLAN

STUDY PROTOCOL

Potential participants completed a phone screening with an independent evaluator (IE) to determine preliminary study eligibility (Figure 1). Those deemed likely eligible provided consent and were invited to complete a baseline evaluation via video conference, during which the IE administered the MINI, TDI, and NIMH-TSS. The participants also completed the MGH-HS and MIST-A online. Eligible participants were randomly assigned (via block randomization with a 2:1 ratio) to one of the following two conditions: 1) prototype wrist-worn motion detection device and accompanying app (n=10; Figure 2) or 2) reminder bracelet (n=5). Unequal sample sizes were obtained due to the exploratory nature of the comparison, and because the primary focus of the pilot trial was to test the usability, acceptability, and feasibility of device and app, rather than compare the device and app combination to the reminder bracelet. All participants were informed they would receive either a wrist-worn device and accompanying phone app or a stand-alone wrist-worn device. They were told that the two devices would be compared to assist researchers with the continued product development. The IE was masked to treatment assignment.

After randomization, participants were exposed to either the device and app or the reminder bracelet for 4 weeks. A short, four-week intervention period was chosen because past studies that evaluated AEDs led to near-zero levels of hair pulling (Rapp et al., 1998) and finger sucking (Ellingson et al., 2000; Stricker et al., 2001; Stricker et al., 2003) almost immediately. At midpoint (2 weeks) and post (4 weeks), participants were reevaluated via videoconference by the IE. At each visit, the IE administered the NIMH-TSS to the participants via a video call. Participants were instructed not to discuss their treatment assignment with the IE. After completing the video call, participants were sent a link to a Qualtrics survey that included the MGH-HS, MIST-A, and a self-report questionnaire. The IE did not have access to the Qualtrics survey until the study was completed.

Device + App Condition

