Participants in the reminder bracelet group received a bracelet that was physically identical to the prototype awareness device in the device and app condition. However, there was no accompanying app and no motion detection ability. Rather than vibrating when hair pulling was detected, the reminder bracelet was pre-programmed to vibrate twelve times per hour at random intervals. This was based on past internal observational data of the average number of times those with hair pulling pulled per hour during the development of the motion recognition algorithm of the device. Participants were told the device would vibrate randomly several times per hour as a reminder not to hair pull. The device was to be worn during all waking hours for four weeks.

STATISTICAL ANALYSIS PLAN

For the usability, acceptability, feasibility, and perceived efficacy, participants completed a 21-question survey and rate each of the areas on a scale of 1 (strongly disagree) to 5 (strongly agree). Mean scores were compiled and examined. To examine the impact of the device and app on hair pulling severity, Wilcoxon signed-rank tests were conducted on pre-post NIMH-TSS and MGH-HS total scores. To examine the preliminary comparison between the device/app system and reminder bracelet, a 2 (group) by 3 (time) mixed analysis of variance (ANOVA) was conducted to determine whether there were significantly greater decreases in the NIMH-TSS and MGH-HS total scores from baseline to post-treatment among participants who were given the device and app relative to the reminder bracelet.

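### Exploratory device/app versus bracelet comparison: report a baseline-adjusted week-4 difference beside the planned mixed ANOVA, because at 10 v 5 a chance baseline imbalance shifts the comparison of changes (minor, cheap improvement)

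*Combined protocol and SAP*

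**What the plan says.** The Statistical Analysis Plan section names one between-arm analysis: "a 2 (group) by 3 (time) mixed analysis of variance (ANOVA) was conducted", applied to the NIMH-TSS and MGH-HS totals. With bracelet users as the comparator, it looks for "significantly greater decreases in the NIMH-TSS and MGH-HS total scores from baseline to post-treatment among participants who were given the device and app". The Study Protocol section gives only two assessments after baseline, at weeks 2 and 4, so the third level of time has to be baseline. No covariate is named.

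On allocation: "Eligible participants were randomly assigned (via block randomization with a 2:1 ratio"), giving 10 device/app and 5 bracelet participants. Stratification on severity is not mentioned.

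Both baseline scores are described before random assignment. At the baseline evaluation there was a video call "during which the IE administered the MINI, TDI, and NIMH-TSS", and "The participants also completed the MGH-HS and MIST-A online".

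The protocol limits the role of the comparison: "Unequal sample sizes were obtained due to the exploratory nature of the comparison", and "the primary focus of the pilot trial was to test the usability, acceptability, and feasibility of device and app".

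**The concern.** In a trial of 15 people the arms can easily start at different severity. An analysis of raw change does not remove that difference unless week-4 scores rise one for one with baseline scores. If the slope of week 4 on baseline is below 1 and the device arm happens to start worse, regression to the mean makes the device look better than it is. If the device arm starts milder, it looks worse. A slope above 1 reverses the direction.

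What is at stake is how the estimate is read. Readers will take from this comparison whether the device/app lowered severity more than the bracelet. The interaction F has 2 df and no direction, so it supplies no effect estimate. The SAP names no estimate that allows for where each arm started.

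**Working it through.** **Inputs from the documents.** Arms of 10 and 5; visits at baseline, week 2 and week 4; no covariate. There is no sample-size, power or effect-size figure to reproduce.

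**Assumptions.** Two-sided 5%, no dropout, normal scores, equal correlation r between visits. The documents give neither r nor SDs, so r runs from 0.3 to 0.9. Let c = SD at week 4 / SD at baseline, and let d be the baseline imbalance (device minus bracelet) in baseline SDs. The slope of week 4 on baseline is rc, which equals r only when c = 1.

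**Step 1: likely size of the imbalance.** k = 1/10 + 1/5 = 0.3, and the SD of d is sqrt(0.3) = 0.548.
- P(|d| > 0.5) = 2(1 - Phi(0.5/0.548)) = 36%
- P(|d| > 0.7) = 2(1 - Phi(0.7/0.548)) = 20%
- P(|d| > 1) = 2(1 - Phi(1/0.548)) = 6.8%

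These hold for each outcome separately.

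**Step 2: effect on the estimate.** With decrease = baseline minus week 4, the expected difference in decrease given d is the true effect + (1 - rc)d. ANCOVA has no such shift if the slope is common to both arms. Given d:
- MSE of the change difference = c²(1 - r²)k + (1 - rc)²d²
- MSE of ANCOVA = c²(1 - r²)(k + d²/11), where 11 = 13 - 2 allows for estimating the slope

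Example with c = 1, r = 0.5, d = 0.5:
- change: 0.75 x 0.3 + 0.25 x 0.25 = 0.2875, RMSE 0.536
- ANCOVA: 0.75 x (0.3 + 0.25/11) = 0.242, RMSE 0.492, a gain of 8%

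**Step 3: range with equal SDs.** Type I error is from simulation with d fixed and no effect (300,000 trials per cell).

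| r | Shift, d = 0.5 | RMSE change v ANCOVA, d = 0.5 | Gain | Interaction type I error, d = 0.5 | Shift, d = 1 | Interaction type I error, d = 1 |
|---|---|---|---|---|---|---|
| 0.3 | 0.35 | 0.629 v 0.542 | 14% | 4.2% | 0.70 | 11.3% |
| 0.5 | 0.25 | 0.536 v 0.492 | 8% | 4.5% | 0.50 | 9.8% |
| 0.7 | 0.15 | 0.419 v 0.406 | 3% | 4.7% | 0.30 | 7.8% |
| 0.8 | 0.10 | 0.344 v 0.341 | 1% | 4.9% | 0.20 | 7.0% |
| 0.9 | 0.05 | 0.244 v 0.248 | -2% | 5.0% | 0.10 | 6.1% |

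ANCOVA stays at about 5% throughout. The interaction test passes 5% at an imbalance of about 0.6 SD; at r = 0.3 it is about 6% at 0.7 SD and about 7.5% at 0.8 SD. Averaged over all randomisations, both tests reject 5.0% with equal SDs and equal covariance.

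**Step 4: where adjustment stops helping.** ANCOVA has the smaller MSE when (1 - rc)² > c²(1 - r²)/11; d cancels.
- c = 1: r < 10/12 = 0.833.
- c = 0.7: every r. At d = 0.5 the gain is 24% to 31% for r from 0.3 to 0.9.
- c = 1.3: r below about 0.51 or above about 0.90. Between these, change is more accurate, by about 3% at r = 0.7.

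**Step 5: slopes that differ by arm.** Take slopes 0.3 (device) and 0.7 (bracelet), d = 0.5. The expected baseline means are +0.167 and -0.333, so the expected week-4 difference is 0.3 x 0.167 + 0.7 x 0.333 = 0.283. The pooled slope is (9 x 0.3 + 4 x 0.7)/13 = 0.423. ANCOVA keeps 0.283 - 0.423 x 0.5 = 0.07 SD, against a shift in change of 0.5 - 0.283 = 0.22 SD. With the slopes exchanged, the sizes are 0.07 and 0.28. Adjustment then removes most of the shift, not all of it.

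**The case against.** **The plan contains no error.** A group-by-time analysis with baseline as a level of time addresses the stated question and is unbiased over randomisations. This stands. A reader might infer from the conditional shift that the planned test is biased or invalid. The documents do not support that: allocation is random, and the shift averages to zero. The 5% error rate does need sphericity and equal covariance across arms. For example, slopes of 0.3 and 0.7 by arm take a change t test to 2.8% or 8.8% over all randomisations, and ANCOVA to 3.8% or 7.5%. So neither method is protected on that count.

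**The comparison carries little weight.** It is declared exploratory, and no decision rule depends on it. This also stands and sets the rank of the point.

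**The gain is small beside the noise.** At a 0.5 SD imbalance and r = 0.7 the shift is 0.15 SD, while the 95% CI half-width is 0.90 for change and 0.86 for ANCOVA. At r = 0.9 they are 0.52 and 0.53. This stands for high r. It is weaker for low r or a shrinking SD. The protocol's reason for a four-week period, that "past studies that evaluated AEDs led to near-zero levels of hair pulling", makes a smaller week-4 SD plausible but does not establish it.

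**Adjustment might seem justified by power.** A reader could draw this from a comparison with the interaction test, but it would be a poor argument. For a 0.8 SD effect, half of it present at week 2, and r = 0.7, power is 34% for the interaction, about 41% for an unadjusted change t test and 44% for ANCOVA. Most of the gain comes from testing one contrast.

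**It is a matter of preference.** This would carry if the ANOVA were to be replaced. It does not count against one added estimate from data already collected.

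**Conclusion.** The point holds as a minor, cheap improvement. The planned analysis is legitimate, but at 10 v 5 its implied baseline-to-week-4 contrast depends on chance imbalance. An imbalance above 0.5 SD arises in 36% of randomisations per scale. With equal SDs and r from 0.3 to 0.9, an imbalance of exactly 0.5 SD shifts the estimate by 0.35 to 0.05 SD without raising the interaction test's error rate. From about 0.6 SD the error rate exceeds 5%, and at 1 SD it is 11% to 6%. It would therefore be wrong to infer that only extreme imbalance disturbs the test.

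The sizes rest on assumed r and SDs. The accuracy gain shrinks as r rises and reverses above about r = 0.83 with equal SDs. The main reason to adjust is to remove the conditional shift; precision comes second. The usability, acceptability and feasibility aims and the within-arm Wilcoxon tests are unaffected.

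**What to change.** Keep the mixed ANOVA. Beside it, for NIMH-TSS and MGH-HS alike and whatever the result, report the week-4 difference between arms from an ANCOVA on that scale's baseline score (12 residual df), with a 95% CI, labelled exploratory. Show baseline mean and SD by arm so that the imbalance can be seen. The SAP is written in the past tense; if the analysis has already been run, label the addition post hoc.

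No new data are needed. The costs are:
- A common linear slope is estimated from 15 people. This multiplies the ANCOVA variance by 1 + d²/(11 x 0.3), which is 1.08 at a 0.5 SD imbalance and 1.30 at 1 SD.
- Accuracy is slightly lower if r exceeds about 0.83 with equal SDs, or lies between about 0.51 and 0.90 when the week-4 SD is 1.3 times baseline.
- The CI is wider at large imbalance with high r: at 1 SD and r = 0.7, half-width 0.95 against 0.90 for change.
- Two more between-arm estimates could be selectively emphasised. Reporting both scales regardless of result limits this risk, and the post hoc label only partly answers it.
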